3.2. Secondary Objectives

The secondary objectives include:

- To estimate the treatment effect of AP01 given 50 mg once daily and 100 mg twice daily on absolute change in % predicted forced vital capacity (FVC) in patients with IPF
- To estimate the treatment effect of AP01 given 50 mg once daily and 100 mg twice daily on absolute change in % predicted Diffusion Capacity for Carbon Monoxide (D_{LCO}) in patients with IPF
- To compare the safety and efficacy of 50 mg once daily vs 100 mg twice daily dosing to provide guidance on dosing regimens for future studies
- To estimate the treatment effect of AP01 given 50 mg once daily and 100 mg twice daily on change in Patient Reported Outcomes (PROs) and cough in patients with IPF
- To estimate the treatment effect of AP01 given 50 mg once daily and 100 mg twice daily on change in the extent of fibrosis and lung volumes as measured by High Resolution Computed Tomography (HRCT) scans in patients with IPF
- To evaluate the following exploratory measurements:
 - Correlation between weekly home spirometry measurements and in-clinic spirometry values
 - Correlation of extent of fibrosis and lung volumes as measured by HRCT at Baseline and Week 24 to other measures of clinical status, e.g. spirometry
 - Change from baseline in serum biomarkers of alveolar epithelial injury (CA19-9 and CA-125).

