5.4. Protocol Deviations

Protocol deviations will be collected and will be categorized as:

- Informed Consent
- Enrollment Criteria
- Dosing
- Concomitant Medications
- Visits/Procedures Required
- Visit Schedule
- Non-compliance
- Regulatory
- Laboratory
- Other

They will also be graded as Major or Minor.

This document is confidential.

SAP Version: 3.0 (15JUL2021)
Controlled Document ID: **3903A.01**, Effective Date 29-Oct-2018
Filing requirements: TMF

Page 20 of 52

Statistical Analysis PlanSponsor: Avalyn Pharma, Inc.; Protocol No.: AP01-002

Major protocol deviations are defined as a subset of protocol deviations that may significantly impact the completeness, accuracy, and/or reliability of the study data or that may significantly affect the subject's rights, safety or well-being. Major protocol deviations will be included in the Clinical Study Report (CSR). These include: Enrollment Criteria (violation of inclusion/exclusion criteria, Informed Consent (informed consent not provided), Dosing (study drug deviation), Non-compliance, Concomitant Medications (administration of prohibit medication) and Other Good Clinical Practice (GCP) deviations. All protocol deviations will be tracked and corrective live actions implemented.

Protocol deviations will be summarized by grade and category for each treatment group and overall in the following ways:

- Patients with Any Protocol Deviations (Major or Minor)
- Patients with Major Deviations Only
- Patients with Minor Deviations Only (i.e. excluding those patients with Major deviations).
- Protocol Deviations Attributable to COVID-19

All protocol deviations will be listed.

This document is confidential.

SAP Version: 3.0 (15JUL2021)
Controlled Document ID: **3903A.01**, Effective Date 29-Oct-2018
Filing requirements: TMF

Page 21 of 52

Statistical Analysis PlanSponsor: Avalyn Pharma, Inc.; Protocol No.: AP01-002

6. General Aspects for Statistical Analysis**6.1. General Methods**

Unless otherwise specified, all data will be summarized by treatment group and overall. A separate summary of data from Part A of will be provided in addition to a full study summary including both Part A and Part B data. Categorical data will be summarized as number and percent of total. Continuous data will be summarized using mean, median, SD and range. Dose response will be evaluated by comparing safety and changes in efficacy variables across the dose regimens.

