The KBILD Questionnaire⁸ is a disease specific questionnaire consisting of 15 items that measures three specific domains: breathlessness and activities (questions 1, 4, 11 and 13), psychological (questions 3, 5, 6, 8, 10, 12 and 14) and chest symptoms (questions 2, 7 and 9). All items are scored on a seven-point response scale (1, 2, 3, 4, 5, 6, 7). The KBILD domain and total score ranges are 0–100; 100 represents the best health status. A KBILD total score can be derived from the 3 domain scores with the addition of question #15. The algorithm for scoring the KBILD Questionnaire is logit-based and described in Sinha et al. 2019⁹.

The KBILD Questionnaire will be completed at Baseline, all subsequent visits and the Follow-up visit. This is a paper-based questionnaire that will be completed by the patient at the relevant visits. The results of the KBILD will be entered into the appropriate eCRF. Appendix Section 14.2 presents the KBILD Questionnaire.

This document is confidential.

SAP Version: 3.0 (15JUL2021)
Controlled Document ID: **3903A.01**, Effective Date 29-Oct-2018
Filing requirements: TMF

Page 33 of 52

Statistical Analysis PlanSponsor: Avalyn Pharma, Inc.; Protocol No.: AP01-002

The following statistics for each KBILD questionnaire data domain and total score will be calculated and summarized by treatment group and displayed in a table:

- Number and percentage of patients in each treatment group that completed each survey at Baseline and at each post-Baseline time point.
- Summary statistics of the total KBILD score and each KBILD domain score at Baseline and at each post-Baseline time point (Week 4, 8, 12, 16, 20, 24, 36, 48, 60, 72 and Follow-Up)
- Summary statistics of the total KBILD score and each KBILD domain score reflecting the absolute change from Baseline to each post-Baseline time point (Week 4, 8, 12, 16, 20, 24, 36, 48, 60, 72 and Follow-Up).

The following plot will be produced for each KBILD domain score and the KBILD total score:

- Mean KBILD domain (or Total) score Change from Baseline (\pm SD) vs. Visit Week (Week 4, 8, 12, 16, 20, 24, 36, 48, 60, 72 and Follow-Up) with lines for each treatment group.

All KBILD Questionnaire data will be presented in a listing.

8.2.3. Change from baseline in the total LCQ score.

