The LCQ Questionnaire¹⁰ is a disease specific questionnaire consisting of 19 items that measures three specific domains: physical (questions 1, 2, 3, 9, 10, 11, 14 and 15), psychological (questions 4, 5, 6, 12, 13, 16 and 17) and social (questions 7, 8, 18 and 19). All items are scored on a seven-point response scale (1, 2, 3, 4, 5, 6, 7). Domain scores are calculated as the total score from items in the domain divided by the number of items in the domain (range 1–7). The total score is the addition of all domain scores (range 3–21). For all domains, the higher the score the better the quality of life (QOL). If there are missing items, domain scores can be prorated by averaging the number of items actually answered. When there are missing data, prorating by domain in this way is acceptable as long as at least 50% of the items were answered (e.g., a minimum of 2 of 4 items).

The LCQ will be completed at Baseline, all subsequent visits and the Follow-up visit. This is a paper-based questionnaire that will be completed by the patient at the relevant visits. The results of the LCQ will be entered into the appropriate eCRF. Appendix 14.3 presents the LCQ.

The following statistics for each LCQ questionnaire domain and total score will be calculated and summarized by treatment group and presented in a table:

- Number and percentage of patients in each treatment group that completed each survey at Baseline and at each post-Baseline time point.
- Summary statistics of the total LCQ score and each LCQ domain score at Baseline and at each post-Baseline time point (Week 4, 8, 12, 16, 20, 24, 36, 48, 60, 72 and Follow-Up)
- Summary statistics of the total LCQ score and each LCQ domain scores reflecting the absolute change from Baseline to each post-Baseline time point (Week 4, 8, 12, 16, 20, 24, 36, 48, 60, 72 and Follow-Up).

The following plot will be produced for each LCQ domain score and the LCQ total score:

This document is confidential.

SAP Version: 3.0 (15JUL2021)
Controlled Document ID: **3903A.01**, Effective Date 29-Oct-2018
Filing requirements: TMF

Page 34 of 52

Statistical Analysis PlanSponsor: Avalyn Pharma, Inc.; Protocol No.: AP01-002

- Mean LCQ domain (or total) score Change from Baseline (\pm SD) vs. Visit Week (Week 4, 8, 12, 16, 20, 24, 36, 48, 60, 72 and Follow-Up) with lines for each treatment group.

All LCQ Questionnaire data will be presented in a listing.

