8.2.4. Change from baseline in cough severity as measured by VAS

The European Respiratory Society Cough Severity VAS⁶ will be completed at Baseline, all subsequent visits and the Follow-up visit. This is a paper-based scale that will be completed by the patient at the relevant visits. The scale will range on a vertical line from 'No Cough' at the bottom to 'Worst Cough Ever' at the top. The patient will put a cross on the line to indicate the severity of their cough in the last 2 weeks. The results of the scale will be measured in millimeters from the bottom of the scale to the marked cross and entered into the appropriate eCRF. Appendix Section 14.1 presents an example of the Cough Severity VAS.

The following statistics for Cough VAS will be calculated and summarized by treatment group and presented in a table:

- Summary statistics of the Cough Severity VAS score at Baseline and at each post-Baseline time point (Week 4, 8, 12, 16, 20, 24, 36, 48, 60, 72 and Follow-Up)
- Summary statistics of the Cough Severity VAS score reflecting the absolute change from Baseline to each post-Baseline time point (Week 4, 8, 12, 16, 20, 24, 36, 48, 60, 72 and Follow-Up).

The following plot will be produced for the Cough Severity VAS:

- Mean Cough Severity VAS Change from Baseline (\pm SD) vs. Visit Week (Week 4, 8, 12, 16, 20, 24, 36, 48, 60, 72 and Follow-Up) with lines for each treatment group.

All Cough Severity VAS score data will be presented in a listing.

8.2.5. Change from baseline in extent of fibrosis and lung volumes as assessed by HRCT

HRCT scans will be obtained to measure the extent of fibrosis and lung volumes at the Baseline visit and the Week 24 visit, or at an early termination visit if the patient does not complete Part A. These scans will be read and interpreted by a central reader.

The following statistics from the HRCT scans will be calculated and summarized by lung region and treatment group and displayed in a table:

- Summary statistics of the extent of fibrosis and lung volumes as assessed by HRCT at Baseline and the Week 24 post-Baseline time point, or separately for early terminations at the post-Baseline time point available.
- Summary statistics of the extent of fibrosis and lung volumes as assessed by HRCT reflecting the absolute change from Baseline to the Week 24 time point, or separately for early terminations at post-Baseline time point available.

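### K-BILD, LCQ and cough VAS have no pre-specified baseline-adjusted arm difference or confidence interval, although estimating the effect on PROs and comparing the regimens are stated objectives

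*SAP*

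**What the plan says.** **Objectives.** SAP 3.2 and Protocol section 2 both aim to estimate the treatment effect of each regimen "on change in Patient Reported Outcomes (PROs) and cough in patients with IPF". A separate objective, looking ahead to later trials, begins "To compare the safety and efficacy of 50 mg once daily vs 100 mg twice daily dosing to provide guidance on dosing regimens for future".

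**Planned PRO analyses.**
- K-BILD (SAP 8.2.2): for the score itself, "Summary statistics of the total KBILD score and each KBILD domain score at Baseline" and at later visits. For change, the item is "Summary statistics of the total KBILD score and each KBILD domain score reflecting the absolute change from Baseline to each post-Baseline time point". Completion counts, a mean ± SD plot by arm and a listing are also planned.
- LCQ (SAP 8.2.3): "The following statistics for each LCQ questionnaire domain and total score will be calculated and summarized by treatment group and presented in a table". The items match those for K-BILD.
- Cough VAS (SAP 8.2.4): "Summary statistics of the Cough Severity VAS score reflecting the absolute change from Baseline to each post-Baseline time point", with the score itself, a plot and a listing, but no completion counts.

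**General rules (SAP 6.1).** "Continuous data will be summarized using mean, median, SD and range". The next sentence is "Dose response will be evaluated by comparing safety and changes in efficacy variables across the dose regimens". It names no estimator, visit or interval.

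**Other endpoints.** Models are written for FVC (8.1), cough frequency from the cough monitor (8.2.1), HRCT (8.2.5) and DLCO (8.2.6). The exploratory home spirometry (9.2) and CA19-9/CA-125 (9.4) are also modelled.

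**The concern.** The PROs are secondary efficacy endpoints, collected at baseline and at every later clinic visit, yet they receive less analysis than the exploratory biomarkers. SAP section 12, which records departures from the protocol's analyses, does not discuss this.

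Two things are at stake. First, the planned output has no contrast between arms and no statement of its uncertainty, so a reader comparing two columns of means cannot tell a signal from noise. Second, visit means use whichever patients have data. SAP 6.3 rules out imputation in summary tables. Protocol 5.6 allows withdrawal in Part A for excessive FVC decline, and Protocol 5.3 calls for discontinuation when an oral antifibrotic is judged necessary. Missingness may therefore be related to worsening. A repeated-measures model uses each patient's earlier scores and is valid under missing at random, a weaker condition than unadjusted available-case means need.

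**Working it through.** **1. The documents' own precision figure.** The only one is for FVC % predicted (Protocol 11.1, SAP 3.5): SD 4.5, 50 per arm, half-width 1.25.

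1.96 × 4.5 / √50 = 1.247, which reproduces 1.25.

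Nothing comparable is given for K-BILD, LCQ or VAS.

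**2. What each section specifies.**

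| Endpoint | Model | Arm difference | Interval |
|---|---|---|---|
| FVC (8.1) | mixed model | to be examined | 95% CI on LS means |
| Cough frequency (8.2.1) | mixed model | to be examined | not stated |
| HRCT (8.2.5) | linear model | to be examined | not stated |
| DLCO (8.2.6) | mixed model | not stated as such | 95% CI on LS means |
| K-BILD, LCQ, VAS (8.2.2–8.2.4) | none | none | none |

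The mixed-model text in Protocol 11.5.1 and at the start of SAP section 8 is attached to FVC and does not reach the PROs. No interval is planned for within-arm PRO change either.

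**3. Precision of an unadjusted arm difference**, in units of the SD of change. Half-width = critical value × √(2/n), with n patients per arm.

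- n = 50, normal: 1.96 × √(2/50) = 0.392; t-based 0.397
- n = 40, t-based: 0.445
- n = 35, t-based: 0.477

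The n of 50 is the planned arm size. The values 40 and 35 are assumptions, shown because efficacy uses the per-protocol set and some patients will leave.

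**4. On the instruments' scales.** The documents give no PRO SDs, so these are assumed, with 50 per arm:

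- K-BILD (0–100), SD 5, 10, 15: ±1.98, ±3.97, ±5.95 points
- LCQ total (3–21), SD 3: ±1.19 points
- VAS, SD 20 to 25 mm: ±7.9 to ±9.9 mm

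**5. Gain from baseline adjustment.** Assume equal variances σ² at baseline and Week 24, with correlation r. The variance of change is 2σ²(1 − r). The residual variance after adjustment is σ²(1 − r²). The ratio is (1 − r²) / [2(1 − r)] = (1 + r)/2.

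| r (assumed) | Variance ratio | SE reduction | Half-width, n = 50 |
|---|---|---|---|
| 0.4 | 0.70 | 1 − √0.70 = 16% | 0.392 × √0.70 = 0.328 |
| 0.5 | 0.75 | 13% | 0.339 |
| 0.6 | 0.80 | 11% | 0.351 |
| 0.7 | 0.85 | 8% | 0.361 |

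**The case against.** The strongest reply is that description is a reasonable choice here. This is an open-label Phase 1b study with safety as its primary objective and no formal hypothesis tests planned. Protocol 11.5.1 lists the PROs only as change from baseline, so the SAP does not contradict it. The PROs are self-reported by patients who know their regimen, and a model does not remove that bias. All of this is correct. It does not explain the gap, because an estimate with an interval is not a test and the same SAP models other endpoints under the same rule.

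The contrast with those endpoints is also less clean than it first looks. For cough frequency and HRCT no interval is stated, and the DLCO model has no baseline covariate and no stated arm difference. Copying an existing paragraph would therefore not deliver the output needed.

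Some stronger readings are tempting, but the documents do not support them.

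- *That the objectives cannot be answered.* The tables give mean and SD of change by arm and visit, and with the number of patients these yield a crude difference and interval. Estimating an effect for each regimen can be read as within-arm change, for which a point estimate is tabulated. The objective also covers cough, and cough frequency is modelled. The objective to compare regimens covers safety and efficacy as a whole and does not rest on the PROs alone.
- *That the tables show completer means that drift as sicker patients leave.* They are available-case means, and SAP 6.4 maps early termination visits to the closest study visit or uses the actual date where possible. Drift is plausible from the withdrawal rules, but no dropout figure is given.
- *That dose selection is compromised.* The Protocol synopsis and section 1.2.4 say the DSMB had already recommended the regimen by October 2020, citing an FVC trend. The SAP is dated July 2021.

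**Conclusion.** The gap is real and limited. SAP 8.2.2 to 8.2.4 pre-specify no baseline-adjusted arm difference and no confidence interval for the three instruments, and the sentence in SAP 6.1 about comparing regimens does not supply one. No planned figure is wrong, no planned output is invalid, and a crude contrast can be recovered by hand. What is lost is a pre-specified, adjusted estimate with its uncertainty for endpoints that the objectives name.

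The missing interval would be about ±0.39 to 0.40 SD of change with all 50 per arm contributing, and ±0.45 to 0.48 SD with 40 to 35. Adjustment would narrow the 50-per-arm interval to roughly 0.33 to 0.36 SD. That gain rests on an assumed correlation of 0.4 to 0.7 and equal variances, neither of which is in the documents. The change is worth making because it is cheap.

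**What to change.** Add one paragraph to SAP 8.2 covering K-BILD total, K-BILD breathlessness and activities, LCQ total and cough VAS:

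- Fit a repeated-measures mixed model of change from baseline to Part A data only (Weeks 4, 8, 12, 16, 20 and 24), so that the Part B regimen switch does not enter.
- Include baseline score, arm, visit, arm-by-visit and the stratification factors: region, and FVC below 50% versus 50% or more of predicted.
- Use an unstructured covariance for the six post-baseline visits (6 × 7 / 2 = 21 parameters), or name another structure, with a stated fallback if the model does not converge. Compound symmetry, as specified for the two cough-monitor visits, should not be carried over by default.
- Report the Week 24 arm difference with a 95% CI as descriptive estimation, without p-values and alongside the planned summaries. Use the per-protocol set with the full analysis set as support, as SAP sections 5 and 8 already provide.
- Add completion counts for the VAS, to match K-BILD and LCQ.

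The cost is the paragraph and a little programming. No patients, visits or data are added. The write-up should say that the estimates remain open to open-label reporting bias.

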8.2.4. Change from baseline in cough severity as measured by VAS

The European Respiratory Society Cough Severity VAS⁶ will be completed at Baseline, all subsequent visits and the Follow-up visit. This is a paper-based scale that will be completed by the patient at the relevant visits. The scale will range on a vertical line from 'No Cough' at the bottom to 'Worst Cough Ever' at the top. The patient will put a cross on the line to indicate the severity of their cough in the last 2 weeks. The results of the scale will be measured in millimeters from the bottom of the scale to the marked cross and entered into the appropriate eCRF. Appendix Section 14.1 presents an example of the Cough Severity VAS.

The following statistics for Cough VAS will be calculated and summarized by treatment group and presented in a table:

- Summary statistics of the Cough Severity VAS score at Baseline and at each post-Baseline time point (Week 4, 8, 12, 16, 20, 24, 36, 48, 60, 72 and Follow-Up)
- Summary statistics of the Cough Severity VAS score reflecting the absolute change from Baseline to each post-Baseline time point (Week 4, 8, 12, 16, 20, 24, 36, 48, 60, 72 and Follow-Up).

The following plot will be produced for the Cough Severity VAS:

- Mean Cough Severity VAS Change from Baseline (\pm SD) vs. Visit Week (Week 4, 8, 12, 16, 20, 24, 36, 48, 60, 72 and Follow-Up) with lines for each treatment group.

All Cough Severity VAS score data will be presented in a listing.

8.2.5. Change from baseline in extent of fibrosis and lung volumes as assessed by HRCT

HRCT scans will be obtained to measure the extent of fibrosis and lung volumes at the Baseline visit and the Week 24 visit, or at an early termination visit if the patient does not complete Part A. These scans will be read and interpreted by a central reader.

The following statistics from the HRCT scans will be calculated and summarized by lung region and treatment group and displayed in a table:

- Summary statistics of the extent of fibrosis and lung volumes as assessed by HRCT at Baseline and the Week 24 post-Baseline time point, or separately for early terminations at the post-Baseline time point available.
- Summary statistics of the extent of fibrosis and lung volumes as assessed by HRCT reflecting the absolute change from Baseline to the Week 24 time point, or separately for early terminations at post-Baseline time point available.

The following plot will be produced for extent of fibrosis and lung volumes as assessment by HCRT:

This document is confidential.

SAP Version: 3.0 (15JUL2021)
Controlled Document ID: **3903A.01**, Effective Date 29-Oct-2018
Filing requirements: TMF

Page 35 of 52

Statistical Analysis PlanSponsor: Avalyn Pharma, Inc.; Protocol No.: AP01-002

- Mean Extent of Fibrosis (or Lung Volume) Change from Baseline (\pm SD) vs. Weeks from Baseline (calculated based on visit date) for each lung region with lines for each treatment group.

A linear model will be used and differences between treatment groups between the change from baseline in whole lung extent of fibrosis and whole lung volume from Baseline to post-Baseline will be examined. Change from baseline will be the dependent variable and baseline whole lung extent of fibrosis (or whole lung volume), region, age at screening, sex, baseline D_{LCO} % predicted and baseline progression-related biomarker (CXCL13, CCL18, MMP3) values each categorized as $>$ Median level vs. \leq Median level, and time of HRCT (relative to baseline) will be included as covariates in the model.

All HRCT scan data will be presented in a listing including early termination and unscheduled visits.

8.2.6. Change from baseline in D_{LCO}

D_{LCO} will be collected at each visit. For predicted normal values, different sites may use different prediction formulas, based on the method used to measure D_{LCO} . In any case, the method used must be in compliance with the ATS/ERS guidelines⁵ on D_{LCO} measurements and the prediction formula appropriate for that method⁷. Raw data (gas mixture, equation used for prediction of normal, further adjustments made if so) must be traced.

PFTs will be collected at Screening, Baseline (pre-dose and post-dose) and at each Post-Baseline time point (Week 4, 8, 12, 16, 20, 24, 36, 48, 60, 72 and Follow-Up) as described in Section 6.1.

The following statistics for D_{LCO} and D_{LCO} % Predicted will be calculated and summarized by treatment group and displayed in a table:

- Summary statistics of D_{LCO} and D_{LCO} % Predicted at Baseline and at each post-Baseline time point (Week 4, 8, 12, 16, 20, 24, 36, 48, 60, 72 and Follow-Up)
- Summary statistics of D_{LCO} and D_{LCO} % Predicted reflecting the absolute change from Baseline to each post-Baseline time point (Week 4, 8, 12, 16, 20, 24, 36, 48, 60, 72 and Follow-Up).

The following plot will be produced for D_{LCO} and D_{LCO} % Predicted:

- Mean D_{LCO} (or D_{LCO} % Predicted) Change from Baseline (\pm SD) vs. Visit Week (Week 4, Week 8, Week 12, etc.) with lines for each treatment group.

A linear mixed-effects model (PROC MIXED) will be used for the analysis. The model will include the change from baseline in D_{LCO} (or D_{LCO} % Predicted) (measured at any time in the study) as the dependent variable and will include patient as a random effect, fixed effect of time and time-varying effects for treatment group and treatment-by-time interaction to account for those patients who switched dosing regimens from 50 mg once daily to 100 mg twice daily in Part B. To account for correlated repeated measures within patients a spatial power matrix will be used. Longitudinal plots at selected timepoints displaying the model adjusted, least square means and 95% confidence intervals will be produced.

All D_{LCO} data will be presented in a listing.

This document is confidential.

Statistical Analysis PlanSponsor: Avalyn Pharma, Inc.; Protocol No.: AP01-002

9. Exploratory**9.1. Correlation between weekly home spirometry measurements and in-clinic spirometry**

Patients will obtain spirometry readings at home on the same day and at approximately the same time each week (+/- 2 hours). Home spirometers will be dispensed at the Baseline visit; patients will be trained on the use of home spirometers prior to their departure from the Baseline visit. Home spirometer training and accountability data will be presented in a listing.

The home spirometry measurements (FVC, FVC % predicted) will be summarized by treatment group and visit including change from the baseline in-clinic pre-dose spirometry value using descriptive statistics. For the tabular summary and graphical summary, biologically implausible values and outliers will be removed as described previously in Section 8.1. The remaining spirometry measurements (FVC, FVC % predicted) within the mapping window for a scheduled visit will be averaged. All home spirometry data will be included in a listing.

Bland-Altman plots will be produced to describe the agreement between the home and in-clinic spirometry measurements at each visit. In these plots, the average of home spirometry measurements within the mapping window for a scheduled visit will be compared with the in-clinic spirometry at each visit.

A linear mixed-effects model (PROC MIXED) approach¹² will be used to determine the repeated-measures correlation coefficient estimates for in-clinic FVC measurements with averages of home FVC measurements across visits for each treatment group. A normal approximation will be used to determine the estimate for the correlation coefficient (ρ_{hat}), the 95% confidence intervals for the correlation coefficient estimate and p-value. This analysis for Part B will only use measurements in the 50 mg once daily group taken prior to the switch to the 100 mg twice daily group if the patient switched dosing regimens.

9.2. Change in absolute FVC % predicted from home spirometry Baseline visit to Week 24 and Week 72

A linear mixed-effects model (PROC MIXED) will be used for analysis. The model will include FVC % predicted (measured at home) as the dependent variable and will include patient and time of spirometry reading (study day) as random effects, and fixed effects of treatment group, time of spirometry reading (study day), along with a treatment-by-time interaction. Longitudinal plots at selected timepoints displaying the model adjusted, least square means and 95% confidence intervals will be produced. Spirometry data collected after patients switched dosing regimens from 50 mg once daily to 100 mg twice daily will be omitted for this analysis.

9.3. Correlation of extent of fibrosis and lung volume as measured by HRCT at Baseline and Week 24 to other measures of clinical status

The following HRCT measurements will be correlated with the following In-Clinic Spirometry Measurements (FVC) at Baseline and Week 24 or early termination:

- Extent of Fibrosis as Measured by HRCT with FVC

This document is confidential.

Statistical Analysis Plan

Sponsor: Avalyn Pharma, Inc.; Protocol No.: AP01-002

- Lung Volume as Measured by HRCT with FVC.
- Change in Extent of Fibrosis as Measured by HRCT with Change in FVC
- Change in Lung Volume as Measured by HRCT with Change in FVC

A linear mixed-effects model (PROC MIXED) will be used for the analyses of the absolute measures. The models will include the Extent of Fibrosis (or Lung Volume) (measured at Baseline and Week 24 or early termination) as the dependent variable and will include patient as a random effect, and fixed effects of treatment group, FVC (Baseline, Week 24 or early termination), visit, timing of HRCT in weeks from Baseline, and a treatment-by-visit interaction. To account for correlated repeated measures within patients a compound symmetric variance-covariance matrix will be used. Longitudinal plots at selected timepoints displaying the model adjusted, least square means and 95% confidence intervals will be produced. A linear model will be used for the change in Extent of Fibrosis (or Lung Volume). The model will include the change from baseline in Extent of Fibrosis (or Lung Volume) (measured at Week 24 or early termination) as the dependent variable and will include fixed effects of change from baseline in FVC, treatment group, baseline Extent of Fibrosis (or Lung Volume), and timing of HRCT in weeks from Baseline. The model adjusted, least squares mean and 95% confidence interval at Week 24 will be produced.

A linear mixed-effects model will be used to determine the repeated-measures correlation coefficient estimate for Extent of Fibrosis (or Lung Volume) with FVC across visits (Baseline, Week 24) for each treatment group. A normal approximation will be used to determine the estimate for the correlation coefficient (ρ_{hat}), the 95% confidence intervals for the correlation coefficient estimate and p-value. A partial correlation coefficient will be used to determine the correlation coefficient estimates for change in Extent of Fibrosis (or Lung Volume) with change in FVC for each treatment group. The corresponding 95% confidence intervals and p-values for the correlation coefficient estimates also will be reported.

9.4. Change from baseline in serum biomarkers of alveolar epithelial injury (CA19-9 and CA-125)

The serum biomarkers of alveolar epithelial injury (CA19-9 and CA-125)¹¹ will be collected at Baseline, all subsequent visits and the Follow-up visit. The following statistics for CA19-9 and CA-125 will be calculated and summarized by treatment group and displayed in a table:

- Summary statistics of CA19-9 and CA-125 at Baseline and at each post-Baseline time point (Week 4, 8, 12, 16, 20, 24, 36, 48, 60, 72 and Follow-Up)
- Summary statistics of CA19-9 and CA-125 reflecting the absolute change from Baseline to each post-Baseline time point (Week 4, 8, 12, 16, 20, 24, 36, 48, 60, 72 and Follow-Up).

The following plot will be produced for CA19-9 and CA-125:

- Mean CA19-9 (or CA-125) Change from Baseline (\pm SD) vs. Visit Week (Week 4, Week 8, Week 12, etc.) with lines for each treatment group.

Change from baseline in CA19-9 and CA-125 will be correlated with change from baseline in FVC at Weeks 4, 8, 12, 16, 20, 24, 36, 48, 60, and 72. Linear mixed-effects models (PROC MIXED) will be used for the analyses. The model will include the change from baseline in CA19-9 (or CA-125) (measured at Weeks 4, 8, 12, 16, 20, 24, 36, 48, 60, and 72) as the dependent variable and will include patient as a

This document is confidential.

Statistical Analysis PlanSponsor: Avalyn Pharma, Inc.; Protocol No.: AP01-002

random effect, fixed effects of time, change from baseline in FVC (measured at Weeks 4, 8, 12, 16, 20, 24, 36, 48, 60 and 72), baseline CA19-9 (or CA-125), visit and time-varying effects for treatment group and treatment-by-time interaction to account for those patients who switched dosing regimens from 50 mg once daily to 100 mg twice daily in Part B. To account for correlated repeated measures within patients a spatial power variance-covariance matrix will be used. Longitudinal plots at selected timepoints displaying the model adjusted, least square means and 95% confidence intervals will be produced.

A linear-mixed effects model (PROC MIXED) approach will be used to determine the repeated-measures correlation coefficient estimates for change from baseline in CA-19 (or CA-125) with change from baseline in FVC for each treatment group using change from baseline at Weeks 4, 8, 12, 16, 20, 24, 36, 48, 60 and 72. A normal approximation will be used to determine the estimate for the correlation coefficient (ρ_{hat}), the 95% confidence intervals for the correlation coefficient estimate and p-value. Spirometry data collected after patients switched dosing regimens from 50 mg once daily to 100 mg twice daily will be omitted from this analysis.

This document is confidential.

SAP Version: 3.0 (15JUL2021)
Controlled Document ID: **3903A.01**, Effective Date 29-Oct-2018
Filing requirements: TMF

Page 39 of 52

Statistical Analysis PlanSponsor: Avalyn Pharma, Inc.; Protocol No.: AP01-002

10. Safety

The population used for safety analyses will be the SAF. Safety will be assessed on the basis of AE or adverse drug reactions (ADR) reports, clinical laboratory data, ECG parameters, physical examinations, vital signs and change from pre-dose to post-dose FEV₁ after initial dose.

Treatment-emergent AEs (any AEs recorded during or following the first study drug administration) will be summarized by treatment group and categorized by severity and relationship to the study procedures and to the investigational product (IP). If a patient has more than 1 occurrence of the same AE, he/she will be counted only once within that preferred term in the summary tables. The most severe occurrence of an AE, as well as the most extreme relationship of the AE to the study procedures and IP, will be indicated in cases of multiple occurrences of the same AE. SAEs will be summarized separately.

All AE data will be presented in a listing. Additionally, listings of SAEs and AEs leading to discontinuation will be generated. All SAEs will be evaluated to determine whether they are SUSARs or Unexpected Adverse Device Effects.

